5.4 Accrual

We will enroll at least 480, and up to 720, adults from 60 neighborhood microclusters in the study, half of which will be randomized to the intervention and half to the control. If more than one household resident is interested and eligible in the study, the person with the most recent birthday will be enrolled. One participant per household is eligible.

If there are one or more children ages 3-17 living in the household, this child's caregiver will also be given the option of completing an additional survey regarding their child's health. We will enroll adult caregivers of 480 children ages 3-17, including the 480 adults described above and up to 240 additional participants.

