5.6 Key exclusion criteria

- 1. Individuals who plan to move out of the study microcluster within 6 months
- 2. Individuals who are unable to fully consent and participate based on CC team assessment
- 3. Individuals who are not the primary caregivers of children ages 3-17 years

6. Subject recruitment

Participant recruitment will commence in September 2022 and will run through March 2024. Recruitment in control and intervention microclusters will occur simultaneously. The data analyst who performed the randomization will randomize microcluster order (stratified by intervention and control status and city section) to determine the order in which recruitment occurs.

Several Community Coordinator (CC) teams will be recruiting participants. A given team of two will remain in a microcluster until a total of 12 participants are fully enrolled in that microcluster. They will then move to the next microcluster on the randomly generated list. Multiple microclusters will be undergoing enrollment simultaneously. The CC team will be blinded to what arm of the trial the microcluster is in until all participants are enrolled. Participants will also be blinded until after everyone in that cluster is enrolled.

When starting recruitment in a new microcluster, the CC team will first place door knockers on all homes within the microcluster boundaries to alert neighbors to the presence of the study team in the neighborhood. They will then begin door-to-door recruitment at a pre-determined house that is closest to the geographic center of the study microcluster. They will follow a pre-determined route throughout the neighborhood that includes walking up one side of the street and back down the other side of the street before moving on to an adjacent block, and the next adjacent block, etc. The block order will be pre-determined by the data analyst performing randomization to where blocks will be ordered as closet to concentrically in a clockwise manner from the first block.

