Within the city section strata, we conducted a covariate-constrained randomization process in order to ensure balance between microclusters randomized to intervention and those randomized to control based on relevant sociodemographic variables. Covariate-constrained randomization quantifies baseline imbalance of microcluster-level covariates (both categorical and continuous) across all microclusters using a balance metric and then randomly selects one randomization schema from those with acceptable balance. Furthermore, the intraclass correlation coefficient calculation – a measure of reliability – remains unaffected under a constrained randomization model.²

We chose the following covariates to balance on: age (categorized by shares under age 19, 19-49, 50-64, and 65 and above); gender; median income; unemployment rate; amount of vacancy; and tree canopy. We did not balance on race/ethnicity (e.g., % Black) or poverty rates, since initial criteria for study site selection focused on census tracts whose populations were at least 80% Black and with elevated poverty rates. The covariates were measured based on their distribution of means by each microcluster using block group data from the US Census Bureau's 2020 ACS. Each microcluster's mean is the weighted mean for the covariates based on percent of land area in each census block group in which the microcluster sits. A microcluster could be in one census block group or could cross over 2 or 3 census block groups. Following the literature, we used a threshold of 0.2 for standardized mean differences in the covariates.

We used the -cvcrand- package, specifically the -cvrall- function, in R to calculate the final covariate balance metric and selection schema at random after covariate balance by cluster was achieved.²

Enrollment

Participant recruitment will commence in September 2023 and will run through May 2023 (or until we enroll at least 480, but no more than 720, in the main trial). Recruitment in control and intervention microclusters will occur simultaneously. The data analyst who performed the randomization will randomize microcluster order (stratified by intervention and control status and city section) to determine the order in which recruitment occurs.

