Several Community Coordinator (CC) teams will be recruiting participants. A given team of two will remain in a microcluster until at least 8participants are fully enrolled in that microcluster. They will then move to the next microcluster on the randomly generated list. Multiple microclusters will be undergoing enrollment simultaneously. The CC team will be blinded to what arm of the trial the microcluster is in until all participants are enrolled. Participants will also be blinded until after everyone in that cluster is enrolled.

When starting recruitment in a new microcluster, the CC team will first place door knockers on all homes within the microcluster boundaries to alert neighbors to the presence of the study team in the neighborhood. They will then begin door-to-door recruitment at a pre-determined house that is closest to the geographic center of the study microcluster. They will follow a pre-determined route throughout the neighborhood that includes walking up one side of the street and back down the other side of the street before moving on to an adjacent block, and the next adjacent block, etc. The block order will be pre-determined by the data analyst performing randomization to where blocks will be ordered as closet to concentrically in a clockwise manner from the first block.

For a given house, a potential participant will be screened by the CC team to determine eligibility:

Key Inclusion Criteria:

- At least 18 years of age
- Have the ability to communicate via text messaging

- Individuals comfortable communicating in English
- A permanent resident of the home where they are to be enrolled
- Have knowledge of their household finances

Key Exclusion Criteria:

- Individuals who plan to move out of the study microcluster within 6 months
- Individuals who are unable to fully consent and participate based on CC team assessment

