If more than one household resident is interested and eligible in the study, the person with the most recent birthday will be enrolled. One participant per household is eligible. The CC team will conduct an informed consent with all participants. The CC team will then administer a demographic and baseline survey and directly enter data into REDCap. Participants will be compensated \$40 after the baseline survey using ClinCards, \$15 after a 6 month check in, \$15 after a 12 month check in, \$15 after an 18 month check in, and \$40 after a follow up survey. Follow up data collection will occur between September 2024 and March 2025, with each participant surveyed roughly 24 months after their initial enrollment date.

For all households including one or more children ages 3-17 living in the household, the child or children's primary caregiver will be asked to complete an additional follow-up survey regarding their child's health and well-being, for up to three children per household. If more than three children ages 3-17 reside in the household, the enrolled caregiver will be asked to complete the survey for the three children with the most recent birthdays. Participants who complete the follow-up survey regarding children's health will be compensated \$20 after survey completion.

To support recruitment efforts, we will partner with community organizations to widen the reach of study promotion and to improve dissemination of recruitment materials, particularly in communities where recruitment is found to be difficult. We will also use a community-facing website to promote the study and increase screening for enrollment.

Respondent Driven Sampling

IGNITE referrals. Respondent driven sampling will be implemented to drive enrollment when Community Coordinators identify that completing enrollment (i.e., reaching at least 8 participants) is difficult in a particular microcluster. This strategy will be implemented only as a contingency.

Participants will then be invited to refer individuals who they think may be willing to participate in the study. If those referrals meet eligibility criteria and are successfully enrolled, the participant who made the initial referral will receive a payment of \$10 via their ClinCard for that successful referral.

Participants can make an unlimited number of referrals, but only up to 2 referrals will be enrolled per participant (to limit referral networks at a max of four networks per cluster.)

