For this cluster randomized trial, we assume a Type I error rate of 0.05 and a desired power of 0.8 for the primary outcomes. Our study will include 60 microclusters (30 intervention, 30 control) with at least 8 participants in each cluster (n=480 across all clusters). We will have no fewer than 480 and can enroll up to 720. The number of participants enrolled will depend on our dynamic enrollment strategy that we've discussed already. We assume an intraclass correlation (ICC) of 0.05. For our primary outcomes (and all survey-based outcomes), we will fit a marginal model using generalized estimating equations (GEE) to estimate the effect of the intervention relative to control. Under these assumptions, we will be able to detect an intervention effect of 0.33 s.d at 80% power with 30microclusters per arm (60 total) and 8 participants per microcluster.⁹ This is a conservative estimate of power since we will adjust for the baseline value of the outcome and other covariates associated with the outcome. If we are only able to sample from 50 microclusters (25 per arm; n=400 across all clusters), we will be able to detect a moderate effect size of 0.37 s.d. at 80% power. Assuming up to 25% attrition between baseline and endline, we would still be able to detect a treatment effect of 0.31 s.d.

Statistical Analysis

Individual-level primary and secondary outcomes

For all primary and secondary outcomes drawn from our two-wave survey of 720 trial participants, we will assess differences in outcomes between the intervention and comparison groups using Generalized Estimating Equation models (GEE) that account for clustering at the study microcluster level. We will use canonical link functions for all outcomes. All models will adjust for the baseline level of the outcome, all microcluster-level characteristics used in the covariate constrained randomization (see randomization protocol),¹⁰ any individual characteristics found to be imbalanced between the intervention and control groups at baseline.

We will conduct an intention-to-treat analysis: participants that move out of (or across) study clusters, separately engage with community partner services while in the control group, or do not engage with these services while in the treatment group will all be considered exposed to their original treatment assignment.

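### Sections 6 and 8.2 give different per-cluster enrolment rules (12 versus at least 8), and the detectable effect stated after 25% attrition (0.31 SD) is smaller than the one stated for 60 × 8 without it (0.33 SD)

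*Combined protocol and SAP*

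**What the plan says.** **Enrolment rule.** Section 6 (Subject recruitment) states: "A given team of two will remain in a microcluster until a total of 12 participants are fully enrolled in that microcluster". Section 8.2 (Enrollment) repeats the instruction as: "A given team of two will remain in a microcluster until at least 8participants are fully enrolled in that microcluster". In both places the team then moves to the next microcluster on the list. The contingency for referral sampling in Section 8.2 also treats 8 as completion; it applies when "completing enrollment (i.e., reaching at least 8 participants) is difficult in a particular microcluster".

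**Total.** Section 5.4 says "We will enroll at least 480, and up to 720, adults from 60 neighborhood microclusters in the study", and Section 8.2 runs recruitment "or until we enroll at least 480, but no more than 720, in the main trial". Power Calculations in Section 9 gives the same range and attributes it to a dynamic enrolment approach said to have been discussed already.

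**Section 9.** Power Calculations uses 30 microclusters per arm, at least 8 participants each (n=480), ICC 0.05, a Type I error rate of 0.05 and 80% power. It states a detectable effect of 0.33 SD for 60 × 8 and 0.37 SD for 50 × 8. It then says that with up to 25% attrition "we would still be able to detect a treatment effect of 0.31 s.d". No cluster count, cluster size or alpha is attached to that last figure. Statistical Analysis then refers to outcomes "drawn from our two-wave survey of 720 trial participants".

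**The concern.** Two versions of one field instruction carry different numbers, and the approach meant to link them is not set out anywhere in the document. The stop also fixes other events: the team and participants learn the cluster's arm once enrolment there is complete, and caregiver-only recruitment begins after adult enrolment closes. Two teams reading different sections could therefore act differently on all three.

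The power paragraph has a separate problem. With everything else fixed, losing participants must raise the detectable effect, yet the figure falls from 0.33 to 0.31 SD. A reader relying on 0.31 SD would credit the trial, at its committed minimum of 480, with more sensitivity than the stated inputs give.

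**Working it through.** **Inputs (Section 9, Power Calculations).** k = 30 clusters per arm; ICC = 0.05; alpha = 0.05; power = 0.80; m = 8 enrolled per cluster; attrition 25%. Sidedness is not stated, so I assume two-sided. I also assume attrition is spread evenly over clusters. The text credits no covariate adjustment; it offers adjustment as the reason its figure is conservative.

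**Totals.** 60 × 8 = 480 and 60 × 12 = 720. After 25% loss, 8 becomes 6 and 12 becomes 9.

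**Formula.** MDE = C × sqrt(2 × [1 + (m − 1) × ICC] / (k × m)). At two-sided 0.05, C = 1.960 + 0.842 = 2.802 (normal), or 2.002 + 0.848 = 2.850 (t, 58 df).

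**The plan's own pre-attrition figures first.**
- 60 × 8: design effect 1 + 7 × 0.05 = 1.35; sqrt(2 × 1.35 / 240) = 0.1061; MDE = 0.297 (normal) to 0.302 (t). The stated 0.33 is not reproduced.
- 50 × 8: MDE = 0.326 to 0.332. The stated 0.37 is not reproduced.

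Two readings come close:
- Alpha 0.025, which the document does not state, with 8 per cluster and t critical values: 0.334 and 0.368. These round to 0.33 and 0.37.
- Alpha 0.05 with 6 completers per cluster: 0.330 (normal) to 0.336 (t) for 60 clusters, and 0.362 to 0.369 for 50. The ranges cover the stated figures, although 0.33 is met by the normal value and 0.37 by the t value. On this reading the 25% loss is already included.

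**Post-attrition and 12-per-cluster figures (60 clusters, two-sided 0.05).**

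| Per cluster | Design effect | SE of the difference (SD units) | MDE, normal to t |
|---|---|---|---|
| 8 enrolled | 1.35 | 0.1061 | 0.297–0.302 |
| 6 retained of 8 | 1.25 | 0.1179 | 0.330–0.336 |
| 12 enrolled | 1.55 | 0.0928 | 0.260–0.264 |
| 9 retained of 12 | 1.40 | 0.1018 | 0.285–0.290 |

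Power for 0.31 SD with 6 retained: 0.31 / 0.1179 = 2.63. Then 2.63 − 1.96 = 0.67 gives 0.75 (normal), and 2.63 − 2.00 = 0.63 gives 0.73 (t). With 9 retained, power is 0.86 (normal) or 0.85 (t).

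At alpha 0.025, 6 retained gives 0.363 to 0.371 and 9 retained gives 0.314 to 0.321. From 60 × 8 less 25%, no two-sided setting gives 0.31; one-sided 0.05 gives 0.293 to 0.297.

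**Settings that do round to 0.31.**
- 60 × 9 completers, alpha 0.025, normal: 0.314.
- 50 × 9 completers, alpha 0.05, normal: 0.313.
- 50 × 12 with no loss, alpha 0.025, normal: 0.313.
- 60 × 7 completers, alpha 0.05, normal: sqrt(2 × 1.30 / 210) = 0.1113; × 2.802 = 0.312. This needs 7 / 0.75 = 9.3 enrolled per cluster, inside the 480–720 range.
- 60 × 6 completers, alpha 0.05, with covariates explaining 1 − (0.31/0.330)² = 0.12 to 1 − (0.31/0.336)² = 0.15 of the variance.

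**The case against.** The best defence is that the 8 in Section 8.2 is a floor and 12 a ceiling, which is what a total of 480 to 720 implies. The 0.33 SD claim is tied openly to 8 per cluster, and further enrolment can only improve it. The 720 in Statistical Analysis is one descriptive clause on which no model or test depends. Planned baseline adjustment may well bring real sensitivity to 0.31 SD or better.

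Much of this stands. It rules out several stronger readings that a reader might infer:
- *That Section 8.2 yields a trial a third smaller than Section 6.* That is the extreme case, with every cluster stopping at exactly 8; the text sets a minimum.
- *That Section 9 as a whole assumes 720.* Power Calculations uses 480 explicitly.
- *That 720 must mean 60 × 12.* Section 5.4 also describes 480 adults plus up to 240 additional caregivers, and 480 + 240 = 720. The Abstract mentions up to 720 households.
- *That 0.31 SD is left over from a 12-per-cluster design.* Several routes reach 0.31. The 9-retained route does so only at an unstated alpha and with normal critical values; its t value is 0.321. That alpha also sits awkwardly with a plan that prefers stacked GEE to Bonferroni-Holm.

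The defence does not explain when a team between 8 and 12 leaves, or why the figure falls after attrition. Covariate adjustment cannot be assumed silently in one figure when the paragraph says it was left out.

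**Conclusion.** The inconsistency holds on the text. Section 6 sets 12, Section 8.2 sets at least 8, the linking rule is absent, and Section 9 uses 480 in one place and 720 in another.

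The 0.31 SD figure does not follow from the stated inputs at the 480 minimum. With 6 retained per cluster the detectable effect is 0.33 to 0.34 SD, and power for 0.31 SD is about 0.73 to 0.75 instead of 0.80. This rests on two-sided alpha 0.05, ICC 0.05, even attrition and no covariate credit. The shortfall is modest, and planned adjustment could close it.

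The documents do not show where 0.31 came from, or whether 0.33 and 0.37 reflect alpha 0.025 at 8 per cluster or alpha 0.05 at 6 completers. The matter should be corrected, but it does not undermine the design.

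**What to change.** 1. Put one per-cluster rule in Sections 6 and 8.2. It should say when a team leaves once 8 are enrolled and what the cap is, consistent with 480 to 720. A minimum and a maximum alone would leave the gap between 8 and 12 open.
2. In Statistical Analysis, replace the fixed 720 with the enrolled main-trial participants, and state whether caregivers enrolled only for IGNITE Kids are included.
3. Restate the pre- and post-attrition detectable effects at the 480 minimum, and at 720 if wanted. Name the clusters, completers per cluster, alpha and its sidedness, and any covariate adjustment beside each figure.

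The cost is wording, and a less favourable post-attrition figure at the minimum size. No change to the number of clusters or the analysis model is needed.

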8.1 Consent

Informed consent will be obtained in person at the participant's home using REDCap, a HIPAA compliant webbased platform. The potential participant will receive information explaining the purpose of the study and what would be required of the participant, and that participation is voluntary. Any questions the potential participant may have will be addressed. The community coordinator team will convey important and relevant information about the study, disclose all risks and benefits, fully describe the study procedures relevant to participants, answer all questions, and enable each participant to make a competent, informed decision about volunteering for the study, free from undue influence.

In response to a global or regional epidemic (e.g., COVID-19) or other extreme circumstances (e.g., natural disaster, medical emergency), the informed consent process may be conducted remotely to minimize potential risks to participants. The informed consent process may also be conducted remotely if participants are interested in the study but are not available during our normal recruitment hours. To aid in this process, a copy of the informed consent form can be provided to the participant in advance of the consent discussion, either in person when they are approached at their residence or via email. The informed consent discussion will be conducted via telephone or a video-conferencing platform (e.g., Zoom). To ensure the privacy of the participant, the community coordinator will conduct the remote informed consent process from a private location, while the participant is expected to be in their home. The participant will have ample time to consider their participation and consult with others (e.g., family, friends) prior to signing the informed consent. Once the consent discussion is complete, REDCap will be used to document the participant's consent and capture a hand signature using a

finger, stylus, or mouse. The community coordinator will review the REDCap form to make sure the signature has saved.

8.2 Procedures

Site selection

Census tract selection

We created a list of all census tracts (n=384) in Philadelphia, PA using the 2019 American Community Survey (ACS). Using 5-year population estimates, we determined the total number of Black residents for each tract by combining the number of residents who identified as Black only and Black in addition to one or more races. We then sorted the census tracts based on percent of Black residents from high to low. To ensure that our study focused on predominantly Black neighborhoods, census tracts with a high proportion of Black residents (80% or more of the population; n=99) were deemed eligible for inclusion in the study.

Another goal of the trial is to reach the most economically distressed neighborhoods and households. To achieve this, we included only those census tracts where at least 39% of households had an income at least 200% below Federal Poverty Level (FPL). This threshold mirrors the citywide proportion of families living at 200% or below of FPL. Seventy five of the 99 predominantly Black census tracts met this inclusion criteria (one census tract met this criteria but was excluded as it was in the [name] Philadelphia section of Philadelphia which is geographically dissimilar from the rest of the tracts).

Block random sampling

Neighborhood microclusters (hereafter, microcluster) served as the intervention unit for the study. To form these microclusters, a master list of every block, or street segment from one intersection to the next intersection, in the 75 eligible census tracts was created. A total of 8,462 blocks were included in the master list. A shapefile of selected blocks was imported into R. A random block was chosen as an index block and a 0.125 (one eighth) mile diameter buffer was created around that block. All other blocks that fell within this radius were used to form a microcluster of geographically proximal blocks. A block was included in the microcluster if at least half of the street segment fell within the microcluster boundaries. This microcluster formed a study area. All blocks that were included in the microcluster were removed from the master list to ensure no overlap of microclusters. Next, an additional 0.125-mile exclusion zone buffer was created on all sides of each microcluster. The purpose of the exclusion zone was to create an additional buffer between microclusters to minimize potential spillover effects from the interventions. This process was then repeated until 60 total non-overlapping microclusters were in each city section.

Our goal was to have a final set of microclusters that minimized overlap of microcluster exclusion zones to reduce potential spillover and contamination effects across trial arms. To do this in a random manner, the process to create 60 study microclusters with 0.125-miles exclusionary zones was repeated 1,000 times to create 1,000 unique maps. An analysis was run to determine the total area of exclusion zone buffer overlap for each of the 1,000 microcluster map iterations, which was then ordered from lowest to highest. We then selected the bottom microcluster iterations with the lowest exclusion zone overlap. From this list, one iteration was selected at random to determine final study sites.

Randomization

We randomly assigned the 60 microclusters to treatment (intervention, n=30 microclusters) and control (nonintervention, n=30 microclusters) groups. Prior to randomization, microclusters were stratified by city section (West and North). The land area and number of streets in each section was near-equal, allowing for stratification pre-constrained randomization.¹

Within the city section strata, we conducted a covariate-constrained randomization process in order to ensure balance between microclusters randomized to intervention and those randomized to control based on relevant sociodemographic variables. Covariate-constrained randomization quantifies baseline imbalance of microcluster-level covariates (both categorical and continuous) across all microclusters using a balance metric and then randomly selects one randomization schema from those with acceptable balance. Furthermore, the intraclass correlation coefficient calculation – a measure of reliability – remains unaffected under a constrained randomization model.²

We chose the following covariates to balance on: age (categorized by shares under age 19, 19-49, 50-64, and 65 and above); gender; median income; unemployment rate; amount of vacancy; and tree canopy. We did not balance on race/ethnicity (e.g., % Black) or poverty rates, since initial criteria for study site selection focused on census tracts whose populations were at least 80% Black and with elevated poverty rates. The covariates were measured based on their distribution of means by each microcluster using block group data from the US Census Bureau's 2020 ACS. Each microcluster's mean is the weighted mean for the covariates based on percent of land area in each census block group in which the microcluster sits. A microcluster could be in one census block group or could cross over 2 or 3 census block groups. Following the literature, we used a threshold of 0.2 for standardized mean differences in the covariates.

We used the -cvcrand- package, specifically the -cvrall- function, in R to calculate the final covariate balance metric and selection schema at random after covariate balance by cluster was achieved.²

Enrollment

Participant recruitment will commence in September 2023 and will run through May 2023 (or until we enroll at least 480, but no more than 720, in the main trial). Recruitment in control and intervention microclusters will occur simultaneously. The data analyst who performed the randomization will randomize microcluster order (stratified by intervention and control status and city section) to determine the order in which recruitment occurs.

Several Community Coordinator (CC) teams will be recruiting participants. A given team of two will remain in a microcluster until at least 8participants are fully enrolled in that microcluster. They will then move to the next microcluster on the randomly generated list. Multiple microclusters will be undergoing enrollment simultaneously. The CC team will be blinded to what arm of the trial the microcluster is in until all participants are enrolled. Participants will also be blinded until after everyone in that cluster is enrolled.

When starting recruitment in a new microcluster, the CC team will first place door knockers on all homes within the microcluster boundaries to alert neighbors to the presence of the study team in the neighborhood. They will then begin door-to-door recruitment at a pre-determined house that is closest to the geographic center of the study microcluster. They will follow a pre-determined route throughout the neighborhood that includes walking up one side of the street and back down the other side of the street before moving on to an adjacent block, and the next adjacent block, etc. The block order will be pre-determined by the data analyst performing randomization to where blocks will be ordered as closet to concentrically in a clockwise manner from the first block.

For a given house, a potential participant will be screened by the CC team to determine eligibility:

Key Inclusion Criteria:

- At least 18 years of age
- Have the ability to communicate via text messaging

- Individuals comfortable communicating in English
- A permanent resident of the home where they are to be enrolled
- Have knowledge of their household finances

Key Exclusion Criteria:

- Individuals who plan to move out of the study microcluster within 6 months
- Individuals who are unable to fully consent and participate based on CC team assessment

If more than one household resident is interested and eligible in the study, the person with the most recent birthday will be enrolled. One participant per household is eligible. The CC team will conduct an informed consent with all participants. The CC team will then administer a demographic and baseline survey and directly enter data into REDCap. Participants will be compensated \$40 after the baseline survey using ClinCards, \$15 after a 6 month check in, \$15 after a 12 month check in, \$15 after an 18 month check in, and \$40 after a follow up survey. Follow up data collection will occur between September 2024 and March 2025, with each participant surveyed roughly 24 months after their initial enrollment date.

For all households including one or more children ages 3-17 living in the household, the child or children's primary caregiver will be asked to complete an additional follow-up survey regarding their child's health and well-being, for up to three children per household. If more than three children ages 3-17 reside in the household, the enrolled caregiver will be asked to complete the survey for the three children with the most recent birthdays. Participants who complete the follow-up survey regarding children's health will be compensated \$20 after survey completion.

To support recruitment efforts, we will partner with community organizations to widen the reach of study promotion and to improve dissemination of recruitment materials, particularly in communities where recruitment is found to be difficult. We will also use a community-facing website to promote the study and increase screening for enrollment.

Respondent Driven Sampling

IGNITE referrals. Respondent driven sampling will be implemented to drive enrollment when Community Coordinators identify that completing enrollment (i.e., reaching at least 8 participants) is difficult in a particular microcluster. This strategy will be implemented only as a contingency.

Participants will then be invited to refer individuals who they think may be willing to participate in the study. If those referrals meet eligibility criteria and are successfully enrolled, the participant who made the initial referral will receive a payment of \$10 via their ClinCard for that successful referral.

Participants can make an unlimited number of referrals, but only up to 2 referrals will be enrolled per participant (to limit referral networks at a max of four networks per cluster.)

IGNITE Kids referrals. To support enrollment efforts for the IGNITE Kids sub study, participants may also be asked if they know of and are willing to connect the study team to any families in their neighborhood with children ages 3-17. Participants will be compensated \$10 for successful referrals. Referrals for IGNITE Kids will count towards the 2-referral limit described above.

Tree referrals. To support efforts in planting at least 10 trees in each intervention microcluster, participants will be invited to refer neighbors who may be willing to receive free trees through the study. Referrals may be accepted at the time of enrollment and/or during subsequent home visit(s). Participants will be compensated \$10 for successful referrals. Participants can make and be paid for an unlimited number of tree referrals or for the amount needed until tree planting goals have been met in their particular microluster.

Intervention

Place-Based Interventions

Our suite of place-based interventions consists of four separate interventions which will all be performed simultaneously in all of the intervention microclusters. The four interventions are: vacant lot greening, tree planting, weekly trash pickup, and abandoned house remediation. The first three will be performed through the Pennsylvania Horticultural Society (PHS), while the last will be performed through the City of Philadelphia.

After microclusters have been selected and randomized to the intervention arm (n=30), we will conduct an inventory of the locations of existing vacant lots, abandoned houses, and tree canopy. All place-based interventions will start in April 2023. See below for protocol for each intervention including the intervention timeframe for each.

Vacant lot greening. We will green a total of 150 vacant lots in the intervention microclusters (roughly 3-5 lots totally up to 5000 square feet per microcluster). Vacant lot greening is a standard, reproducible intervention involving (a) the removal of trash and debris, (b) grading of the land, (c) planting new grass and for some lots a small number of trees, and (d) installing a low wooden perimeter fence.³ Vacant lots will be greened between April and June 2023. During the growing season (April-October), bi-monthly maintenance is performed which involves mowing and picking up trash between July 2023 and August 2024. In order to determine which vacant lots will be greened within each microcluster, we will first use a master list of vacant lots provided by PHS and overlay this list with our microcluster boundaries. Vacant lots are eligible for greening if they are in violation of city ordinance (eg. over 10 inches of vegetation) and if they show no signs of active maintenance or ownership (eg. the presence of a locked chain fence). Within each microcluster we will green up to 5 vacant lots totalling up to 5000 square feet of vacant space. We will first eliminate vacant lots over 5000 square feet. If lots in a given microcluster total more than 5000 square feet we will randomly sort the list of vacant lots and select the top 3-5 to total up to 5000 square feet. We will give priority to lots that are contiguous (eg. If a given parcel of land is selected that has 2 other vacant parcels connected to it, we will also include those adjacent parcels before moving down the list to the next vacant lot). If lots in a given microcluster total less than 5000 square feet, we will then inventory vacant lots that are in PHS Community LandCare program, which are vacant lots that receive mowing and trash cleanup, but previously did not receive the full vacant lot treatment described above. We will randomly select vacant lots from this pool to receive the full vacant lot greening treatment to get up to 5000 square feet of vacant lots total in the microcluster. Lots determined eligible by PHS are sent to the City of Philadelphia for permission to green. Some lots sent to the City may ultimately be deemed ineligible and would not receive the greening intervention.

Tree planting. We will plant a total of 300 trees in the intervention microclusters during this study, or roughly 10 trees per cluster. Trees will be planted between September and October 2023, with monthly watering occurring between planting and August 2024 during the growing season. We anticipate that some clusters may receive less than 10 trees and other clusters will receive more than 10 trees based on availability of planting opportunities. Trees will be planted and maintained through PHS. In Philadelphia, permission is needed from the owner of a property to plant a tree. After all participants in an intervention microcluster are enrolled and the microcluster randomization is revealed to the community coordinator team, all participants who indicated they were interested in a tree will have a tree planted in front of their residence based on the following criteria: (a) there is an open space for a tree, (b) there are no physical barriers to tree planting (eg fire hydrant), and (c) the owner of the property lives in the home and is able to give permission to plant a tree. If the participants rents the property, we will determine if they would like to seek permission from the landlord. After we determine which study participants are eligible for a tree, we will then canvas the neighbourhood microcluster to find other residents, businesses, places of worship, etc in the cluster who are not participants in the study who want a tree planted, for a total of 12-15 potential tree planting opportunities. We know that some tree planting sites will

ultimately not be eligible for planting which is why we will initially select 12-15 sites with the aim of planting 10 trees per cluster. This list will then be sent to the PHS who will work with the City of Philadelphia to determine which physical locations are eligible for a tree. For example, sometimes there are water lines too close to the side-walk surface that make a location ineligible.

Trash cleanup. We will provide weekly trash cleanup in all public spaces in the blocks included in our intervention clusters between April 2023 and August 2024. Public space includes on streets and sidewalks, but not into private front yard space. Although the city performs weekly trash pickup, this is limited to trash that is in garbage cans, leaving neighborhoods with a significant trash burden that does not fall under the purview of regular sanitation. Trash cleanup will occur through PHS.

